#### **4.2.2.2 Derivations**

See Section [Definition 4.2.2.1](#).

#### **4.2.2.3 Handling of dropouts and missing data**

Handling of missing TL data is described in Appendix A (Section [7.1](#)).

#### **4.2.2.4 Primary Analysis of Secondary Endpoint**

ORR is based on a subset of all treated participants with measurable disease at baseline per the site investigator.

Summaries are produced that present the number and percentage of participants with a confirmed tumour response (CR/PR). The ORR is presented with a two-sided 90% CI using the Clopper-Pearson (exact probability) method. Participants that have missing OR assessments at all visits are considered as non-responders and are therefore counted in the denominator of ORR. The main analysis of ORR is based on the response evaluable set.

#### **4.2.2.5 Sensitivity Analyses of the Secondary Endpoint**

Sensitivity analysis is NA.

#### **4.2.2.6 Subgroup Analyses**

Subgroup analysis is NA.

### **4.2.3 Best Overall response**

#### **4.2.3.1 Definition**

BOR is calculated based on the overall visit responses from each RECIST v1.1 assessment, described in Appendix A (Section [7.1](#)). It is the best response a participant has had following start of IP, but prior to starting any subsequent cancer therapy and up to and including RECIST v1.1 progression or the last evaluable assessment in the absence of RECIST v1.1 progression. Categorization of BOR is based on RECIST v1.1 using the following response categories: CR, PR, Stable Disease (SD); progressive disease; and NE.

BOR is determined programmatically based on RECIST v1.1. using all site investigator data up until the first progression event (i.e., progression or death). For participants whose progression event is death, BOR is calculated based upon all evaluable RECIST v1.1 assessments prior to death.

#### **4.2.3.2 Derivations**

For participants who die with no evaluable RECIST v1.1 assessments, if the death occurs  $\leq$  15 weeks (i.e. 14 weeks [5 weeks + 9 weeks] + 1 week to allow for a late assessment within the assessment window) after first dose of IP, then BOR is assigned to the progressive disease

category. For participants who die with no evaluable RECIST v1.1 assessments, if the death occurs > 15 weeks after first dose then BOR is assigned to the NE category.

For CR/PR, the initial overall visit assessment that showed a response uses the latest of the dates contributing towards a particular overall visit assessment. A participant is classified as a responder if the RECIST v1.1 criteria for a CR or PR are satisfied at any time following first IP dose, prior to RECIST v1.1 progression and prior to starting any subsequent cancer therapy. CR or PR must be confirmed (see detail in Objective Response Section [4.2.2.1](#)).

For determination of a best response of SD, the earliest of the dates contributing towards a particular overall visit assessment is used. SD should be recorded at least 5 weeks (5 x 7 = 35 days) from first dose.

#### **4.2.3.3 Handling of dropouts and missing data**

Handling of missing TL data is described in Appendix A (Section [7.1](#)). Handling of missing subsequent treatment date is described in section [3.3.6](#).

#### **4.2.3.4 Primary Analysis of Secondary Endpoint**

BOR is summarised by the number and percentage of participants for the following categories: CR, PR, SD, PD and NE. No formal statistical analyses are planned for BOR. The main analysis of BOR is based on the Response evaluable set.

#### **4.2.3.5 Sensitivity Analyses**

Sensitivity analysis is NA.

#### **4.2.3.6 Subgroup Analyses**

Subgroup analysis is NA.

### **4.2.4 Secondary Endpoint: Disease Control Rate at Study Week 15**

DCR at study week 15 is a secondary endpoint.

#### **4.2.4.1 Definition**

Disease control is defined as a BOR of confirmed CR or PR or having SD (without subsequent cancer therapy) maintained for  $\geq 14$  weeks (study week 15) from first IP. Disease control rate at study week 15 weeks (DCR-15) is defined as the percentage of participants who have disease control at study week 15 weeks.

#### **4.2.4.2 Derivations**

A programmed derivation for DCR is:

- If participants have a BOR of confirmed CR or PR, they have disease control.

- Or if a participant has SD to at least DCR time point (i.e., duration of SD  $\geq$  DCR time point), they have disease control. (Note participants with unconfirmed responses should be included in this calculation.)
  - Duration of SD is defined as the time from first IP dose until the first documentation of disease progression or death due to any cause, whichever occurs first:
    - Duration of SD (days) = Disease progression or death or PFS censoring date – first IP dose date +1. SD after the start of subsequent cancer therapy should not be included in this duration.
- Otherwise, they do not have disease control.

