The DCR at 15 weeks is defined as the percentage of participants who have a BoR of CR or PR in the first 16 weeks (to allow for late assessment within the assessment window) or who have SD for at least 14 weeks after the start of treatment (to allow for early assessment within the assessment window). The DCR and its 90% CIs (Clopper Pearson method; Clopper et al, 1934) will be summarised.

Percentage Change in Tumour Size

The percentage change in TL tumour size from baseline will be summarised using descriptive statistics by timepoint. Best percentage change will also be summarised.

Waterfall plots showing the percentage change at 15 weeks and the best percentage change from baseline in sum of the diameters of TLs will be produced. Spider plots showing the percentage change from baseline in tumour size for each participant over time will be produced.

Progression-free Survival

The PFS is defined as the time from the start of study intervention until the date of objective disease progression or death (by any cause in the absence of progression), regardless of whether the participant withdraws from study intervention or receives another anti-cancer therapy prior to progression. Participants who have not progressed or died at the time of analysis will be censored at the time of the latest date of assessment from their last evaluable RECIST assessment.

The PFS time will always be derived, based on scan/assessment dates, not visit dates.

The RECIST assessments/scans contributing towards a particular visit may be performed on different dates. The following rules will be applied:

- Date of progression will be determined, based on the earliest of the dates of the component that triggered the progression.
- When censoring participants for PFS, the participant will be censored at the latest of the dates contributing to a particular overall visit assessment.

Progression-free survival will be summarised descriptively, and Kaplan-Meier plots will be provided.

Overall Survival

Overall survival is defined as the time from the start of treatment until death due to any cause. Any participant not known to have died at the time of analysis will be censored based on the last recorded date on which the participant was known to be alive.

Overall survival will be summarised descriptively, and Kaplan-Meier plots will be provided.

Change in ctDNA

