**Table 1: Timing of analysis**

Analysis	Trigger	Data Type Included
Final analysis	The end of the study is defined as 18 months after the last enrolled participant received his/her first dose of study IP or when the Sponsor stops the study, whichever occurs first.	All data*
Substudy 1		
Interim for efficacy expansions (Parts C1 and C2)	After the 20 th participant in each expansion had the opportunity for 2 on-treatment RECIST assessments	Efficacy (RECIST v1.1 ORR, DoR, DCR at 15 weeks, PFS, OS and tumour size)  Safety
Primary analysis	At completion of each part (primary analysis is conducted separately for each part):	All appropriate data

DCR = disease control rate; DoR = duration of response; IP = Investigational Product; ORR = objective response rate; OS= Overall Survival; RECIST = Response Evaluation Criteria in Solid Tumours v1.1; PFS = Progression Free Survival.

\*Data will be presented by part at the final analysis of the Substudy, except for safety analyses, which will be presented by part and for Part A + Part B if same patients and same dose (See section [4.2](#)).

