#### **4.2.6.2 Derivations**

$$\text{PFS (Months)} = \frac{(\text{Date of PFS event or censoring}-\text{date of first dose of IP})+1}{\left(\frac{365.25}{12}\right)}$$

where PFS event is progression or death.

Participants who have not progressed or died at the time of analysis are censored at the time of the latest date of assessment from their last evaluable disease assessment. However, if the participant progresses or dies immediately after two or more consecutive missed visits, the participant is censored at the time of the latest evaluable disease assessment prior to the two missed visits. Note: a NE visit is not considered as a missed visit.

Given the scheduled visit assessment scheme (i.e., first visit at week six, then nine-weekly for till 52 weeks then twelve-weekly thereafter) the definition of 2 missed visits changes.

If the previous RECIST v1.1 assessment is less than study day 288 (i.e. study week 42) and greater than study day 99 (study week 15), then two missed visits equates to 20 weeks since

the previous RECIST v1.1 assessment, allowing for early and late visits (i.e.  $2 \times 9$  weeks + 1 week for an early assessment + 1 week for a late assessment = 20 weeks).

If the previous RECIST visit is after the visit assessment at study week 6 or study week 15, then two missed visits equate to:

- 15 weeks (105 days), if study week 6 (5 weeks after 1st IP dose) and study week 15 (14 weeks after 1st IP dose) are the two consecutive visits missed [ $(1 \times 5 \text{ weeks}) + (1 \times 9 \text{ weeks}) + 1 \text{ week for late assessment}$ ].
- 19 weeks (133 days), if study week 15 (14 weeks after 1st IP dose) and week 24 (23 weeks after 1st IP dose) are the two consecutive visits missed [ $(1 \times 9 \text{ weeks}) + (1 \times 9 \text{ weeks}) + 1 \text{ week for late assessment}$ ].

If the two missed visits occur over the period when the scheduled frequency of RECIST v1.1 assessments changes from nine-weekly to twelve-weekly this equates to 23 weeks (i.e. take the average of 9 and 12 weeks which gives 10.5 weeks and then apply same rationale, hence  $2 \times 10.5 \text{ weeks} + 1 \text{ week for an early assessment} + 1 \text{ week for a late assessment} = 23 \text{ weeks}$ ). The time period for the previous RECIST v1.1 assessment is from study days 288 to 351 (i.e., study week 42 to study week 51).

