**Table 9: Summary of Censoring Rules for PFS**

Situation	Date of progressive disease /Death or Censoring	PFS Outcome
Documented Progressive Disease or death in the absence of progression	Date of earliest documentation of progressive disease or date of death in the absence of progression	Event
Either no tumour assessment at baseline or no evaluable assessments post-baseline AND death prior to second scheduled post-baseline disease assessment	Date of death	Event
Either no tumour assessment at baseline or no evaluable assessments post-baseline AND no death prior to second scheduled post-baseline disease assessment	Date of first dose (Day 1)	Censored
Progressive disease or death (in the absence of progression) immediately after $\geq 2$ consecutive missed disease assessments as per the protocol specified assessment schedule	Last evaluable progression-free disease assessment prior to missed assessments (if available). Otherwise, the date of censoring is Date of first dose (Day 1)	Censored
On-going with neither progressive disease nor death at the time of analysis or lost to follow-up or withdrawn consent	Date of last evaluable disease assessment	Censored

PFS = progression-free survival

The PFS time is always derived based on scan/assessment dates, and not on visit dates.

RECIST v1.1 assessments/scans contributing towards a particular visit may be performed on different dates. The following rules are applied:

- The date of progression is determined based on the earliest of the dates of the component that triggered the progression.
- When censoring a participant for PFS the participant is censored at the latest of the dates contributing to a particular overall visit assessment.

Note: for TLs only the latest scan date is recorded out of all scans performed at that assessment for the TLs and similarly for NTLs only the latest scan date is recorded out of all scans performed at that assessment for the NTLs.

The number of participants alive and progression free at 3, 6, 9 and 12 months (PFS-3, PFS-6, PFS-9, and PFS-12) is defined as the Kaplan-Meier estimate of PFS at 3, 6, 9 and 12 months.

‘Potential’ duration of follow-up for PFS is applicable only for PFS censored participants and is defined as follows:

$$\text{Potential duration of follow up for PFS (Months)} = \frac{\text{(Date of PFS censoring-date of first dose of IP)} + 1}{\left(\frac{365.25}{12}\right)}$$

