#### 4.2.7.2 Derivations

For visit based summaries, whenever TL tumour size data for each post-baseline assessment (note: or visit at which progression was documented if before the post-line visit) is available then this is used in the analysis. A windowing rule is applied and follows the protocol allowed visit window; therefore, any RECIST v1.1 scan performed within Study W6(D1-D7), W15(D1-D7), W24 $\pm$ 6D then Q9W $\pm$ 6D until W52, then Q12W $\pm$ 6D of the protocol scheduled visit is used for that visit.

The percentage change from baseline in TL tumour size at each post-baseline assessment is obtained for each participant taking the difference between the sum of the TLs at each post-baseline assessment and the sum of the TLs at baseline divided by the sum of the TLs at baseline times 100. For example, the percentage change from baseline in TL tumour size for the post-baseline visit at study week 15 is calculated as follows:

$$\text{Percentage change from baseline in TL tumour size} \\ = \frac{(\text{Study Week 15} - \text{Baseline})}{(\text{Baseline})} \times 100$$

For best percentage change, if it cannot be calculated due to missing data (including if the participant has no TLs at baseline), a value of +20% is imputed as the best percentage change from baseline in the following situations (otherwise best percentage change is left as missing):

- If a participant has no post-baseline assessment and has died;
- If a participant has new lesions or progression of NTLs or TLs;
- If a participant has withdrawn due to progressive disease and has no evaluable TL data before or at progressive disease.

For the outcome endpoint percentage change from baseline in TL tumour size at each post-baseline assessment i.e., Study week 15, participants who progress before study week 15 should have had a tumour assessment performed at the time of progression prior to treatment discontinuation. The tumour size from their latest progression assessment is used instead of the study week 15 assessment for these participants.

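### The SAP's DCR-15 rule counts stable disease at Week 6 followed by progression on the scheduled Week 15 scan as disease control at Week 15

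*SAP*

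**What the plan says.** SAP 4.2.4.1 counts a participant as having disease control with a confirmed CR or PR, or with SD kept for at least 14 weeks from first dose without subsequent cancer therapy. It describes DCR-15 as "the percentage of participants who have disease control at study week 15 weeks".

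SAP 4.2.4.2 turns the SD limb into a calculation: "Duration of SD is defined as the time from first IP dose until the first documentation of disease progression" or death. In days this is the date of progression, death or PFS censoring, minus the first dose date, plus 1. The participant has disease control if the result reaches the DCR time point. Unconfirmed responses go through the same calculation. SD after the start of subsequent therapy is excluded. Nothing in 4.2.4 requires the Week 15 assessment to be free of progression.

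Four other rules matter:

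- **Scan windows** (SAP 4.2.7.2): "RECIST v1.1 scan performed within Study W6(D1-D7), W15(D1-D7"), the same windows as in protocol Table 13.
- **Best response of SD** (SAP 4.2.3.2): "SD should be recorded at least 5 weeks" from first dose.
- **Progression date** (SAP 4.2.6.2, after Table 9): "The date of progression is determined based on the earliest of the dates of the component that triggered the progression".
- **Two missed visits** (SAP 4.2.6.2): if progression or death follows two missed visits, "the participant is censored at the time of the latest evaluable disease assessment prior to the two missed visits".

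Protocol 9.4.3 credits participants "who have SD for at least 14 weeks after the start of treatment (to allow for early assessment within the assessment window"). It does not say whether progression on the Week 15 scan counts.

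**The concern.** DCR-15 is meant to describe disease status at Week 15. The scan that establishes that status is due just after the 98-day threshold has passed. For a participant with SD at Week 6 who reaches that scan, SD and progression on it lead to the same classification. The participants credited in error are those the endpoint should exclude: SD last seen at Week 6, progression found at Week 15.

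DCR at Week 15 is a named secondary efficacy endpoint (protocol Section 3). SAP Table 1 lists it among the Part C interim outputs: "Efficacy (RECIST v1.1 ORR, DoR, DCR at 15 weeks, PFS, OS and tumour size"). SAP Section 5 says the interim should give a reasonable chance of detecting lack of efficacy, and an inflated rate works against that purpose.

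**Working it through.** **Study days.** Cycle 1 Day 1 is study day 1 (SAP 4.2.6.2), so duration = event date − first dose date + 1 = study day of the event.

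- Threshold: 14 × 7 = 98 days.
- Week 15 Day 1: 14 × 7 + 1 = day 99, which reproduces the SAP's own figure for study week 15. Week 15 Day 7: 15 × 7 = day 105.
- Week 6 window: 5 × 7 + 1 = day 36 to 6 × 7 = day 42. This is past the 35-day minimum for a best response of SD.

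**Applying the rule** (no subsequent therapy):

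| Course | End date used | Duration (days) | Credited? |
|---|---|---|---|
| SD at Week 6, SD at Week 15, no later scan | censored at Week 15 scan | 99–105 | yes |
| SD at Week 6, progression at Week 15 | progression at Week 15 scan | 99–105 | yes |
| SD at Week 6, no later scan, alive | censored at Week 6 scan | 36–42 | no |
| SD at Week 6, no later scan, dies on day 120 | death | 120 | yes |

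All seven days of the Week 15 window pass the threshold. A threshold of 99 days would change nothing. A threshold of 105 days would exclude progression on days 99–104, but would also exclude participants censored with SD on those days. Appendix A of the SAP words the schedule as 6 weeks after first dose and then every 9 weeks. That puts the second scan near 15 × 7 + 1 = day 106, with the same result.

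**Deaths.** After a Week 6 scan, two missed visits equal 133 days (SAP 4.2.6.2 and Table 8). A death with only a Week 6 SD scan is credited from day 98 to about day 36 + 133 = 169, or 42 + 133 = 175, depending on the scan day. Later deaths are censored at the Week 6 scan (duration 36–42 days) and are not credited.

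**Size with no PFS assumption.** Each affected participant adds 1/40 = 2.5 points in an expansion of 40 and 1/20 = 5 points if 20 are analysed at the interim.

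**Illustration with assumed counts.** Suppose 12 of 40 truly have disease control at Week 15, and 6 more have SD at Week 6 and progression at Week 15. With Clopper-Pearson 90% intervals:

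- Status at Week 15: 12/40 = 30.0% (18.3 to 44.0).
- As the SAP derives it: 18/40 = 45.0% (31.5 to 59.1).

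**Illustration with assumed exponential PFS.** Scans on days 39 and 102 (window midpoints), a month of 365.25/12 = 30.4375 days, S(t) = exp(−ln 2 × t / median). Inflation = share × [S(39) − S(102)], where the share is the proportion of between-scan events first found on the Week 15 scan.

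| Median PFS | S(39) | S(102) | Share 25% | 50% | 75% | 100% |
|---|---|---|---|---|---|---|
| 2 months | 0.641 | 0.313 | 8 | 16 | 25 | 33 |
| 3 months | 0.744 | 0.461 | 7 | 14 | 21 | 28 |
| 4 months | 0.801 | 0.560 | 6 | 12 | 18 | 24 |

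The last four columns are percentage points. The 100% column is an upper bound. Moving both scans to the window edges gives bounds of 34.0, 28.9 and 24.6 (days 36 and 99) or 31.7, 27.6 and 23.7 (days 42 and 105).

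**The case against.** **Convention and protocol.** Measuring SD up to documented progression is a usual definition of its duration and matches how the SAP dates PFS and DoR. The protocol asks only for SD of at least 14 weeks, so the SAP does not contradict it. That is right, and the upward bias exists only relative to status at Week 15. But Week 15 status is what SAP 4.2.4.1 says is reported, and a duration used as a landmark test fails when the threshold falls just before the scan window opens.

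**Deaths.** A death after one missed scan can be called a missing-data question. It is secondary here, but it follows from the same formula. The upper limit of day 175 relies on the text of SAP 4.2.6.2, since Table 8 lists only study day 36 for the Week 6 row.

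**Interim.** Table 1 lists DCR, but the Interim Response Evaluable set in SAP Table 2 does not. The 5-point figure also assumes exactly 20 analysed, while enrolment continues. Both reservations stand.

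**Size.** The documents give no PFS or DCR assumption. End-of-treatment and unscheduled scans will find some progressions before day 98, and those are correctly not credited. The tabulated inflation is therefore illustrative.

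**Visibility.** There is no hypothesis test, and the same progressions appear in the PFS results, tumour-size plots and listings. This limits the harm but does not correct the DCR.

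**Remedy.** A scan before day 98 showing SD, followed by progression at Week 24, is credited now and would be lost, although the protocol gives early assessment as the reason for 14 weeks. That is a real cost, but such a scan lies outside the Week 15 window of days 99 to 105.

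**Conclusion.** The concern holds. The misclassification follows from the SAP's own threshold, scan window and dating rule and needs no assumption. It affects participants with SD or an unconfirmed response at Week 6, no subsequent therapy, and progression first documented on the scheduled Week 15 scan. It also affects those with only a Week 6 SD scan who die between day 98 and about day 169 to 175. The confirmed CR/PR limb is not in question.

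The only assumption-free size is 2.5 points per affected participant with 40, or 5 with 20. The 30.0% versus 45.0% example rests on assumed counts. The 24 to 33 point upper bounds rest on exponential PFS with medians of 4 to 2 months and on every between-scan event surfacing first at Week 15; deaths before day 98, extra scans and subsequent therapy all lower them. Because DCR-15 is descriptive, the consequence is an overstated rate and interval. It should be fixed before the analysis is programmed or reported.

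**What to change.** In SAP 4.2.4.2, for the SD limb only, replace the duration with: date of the last evaluable non-progressive RECIST assessment before progression, death or subsequent cancer therapy, minus first dose date, plus 1. Keep the threshold of 98 days. Where there is progression or death and no such assessment, classify as no disease control. For an assessment with several scan dates, use the earliest, as SAP 4.2.3.2 already does for SD. Leave the confirmed CR/PR limb unchanged and align the SD wording in protocol 9.4.3.

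SD on the Week 15 scan then has a duration of 99–105 days and still counts. SD at Week 6 followed by progression at Week 15 has 36–42 days and does not.

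The cost is one SAP sentence, one program change and a matching protocol wording. The reported rate will be less favourable. Participants who miss the Week 15 scan, or whose last SD scan was before day 98, will not be counted unless a later scan shows no progression.

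While editing, settle whether DCR is an interim output by reconciling SAP Tables 1 and 2.
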